### **5.6 Discussion and Justification of Study Design**

Subjects who have completed Study M13-550 or Study M13-537 RCT with upadacitinib will be allowed to enroll in the OLE study to continue to receive upadacitinib for up to approximately 312 weeks. The primary objective of OLE study is to collect long-term

safety and tolerability data for upadacitinib. All subjects who roll over into the OLE will be assigned to upadacitinib 6 mg BID initially, regardless of treatment assignment during RCT period, and the basis of this design is to preserve the blinding of treatment assignment in the RCT period. All subjects assigned to 6 mg BID initially will have an option to increase the dose to 12 mg BID (or 30 mg QD from January 2017) throughout the treatment period if a subject is unable to achieve low disease activity with upadacitinib 6 mg BID. At any time during the treatment period, the upadacitinib dose can be decreased back to 6 mg BID (or 15 mg QD from January 2017) per Investigator's judgment if there are safety and tolerability concerns. Those subjects who are unable to achieve at least 20% improvement in both SJC and TJC (minimum clinical efficacy) at defined time-points will be permanently discontinued. This design allows for collection of long-term safety data and avoids continued treatment of those subjects who do not respond to study medication.

From January 2017, all subjects who are at Week 72 or beyond will receive once-daily tablet formulation (15 mg QD or 30 mg QD). Preliminary results of a bioequivalent study demonstrated that single 15 mg and 30 mg doses of the once-daily formulation provide comparable AUC, but significantly lower  $C_{max}$  than single doses of 12 mg immediate release (IR) formulation (equivalent to 6 mg BID dose) and 24 mg IR formulation (equivalent to 12 mg BID dose), respectively. At steady-state, the once-daily dose of 15 mg QD is predicted to achieve comparable daily AUC, lower or comparable  $C_{max}$ , and comparable  $C_{trough}$  to 6 mg BID IR formulation, and the once-daily dose of 30 mg QD is predicted to be equivalent to 12 mg BID IR.

Subjects who are on 6 mg BID (IR) capsule dosing will be transitioned to 15 mg QD tablet dosing. Subjects who are on 12 mg BID dosing will be transitioned to 30 mg QD dosing. Capsule formulation will not be available to the subjects after transition to tablet formulation.

Starting with Amendment 5, subjects who are receiving 30 mg QD open-label upadacitinib will have the option to decrease to the 15 mg QD dose based on investigator's discretion.

### **5.6.1 Appropriateness of Measurements**

Standard statistical, clinical, and laboratory procedures will be utilized in this study. All efficacy measurements in this study are standard for assessing disease activity in subjects with RA. All clinical and laboratory procedures in this study are standard and generally accepted.

### **5.6.2 Suitability of Subject Population**

This OLE study will enroll subjects who have completed Study M13-550 or Study M13-537 RCT with upadacitinib. Only those subjects who have met all of the specified inclusion and none of the exclusion criteria will have an option to enter into the OLE study to receive upadacitinib, as long as the subject is willing and the Investigator believes that continuing the therapy with upadacitinib is appropriate.

### **5.6.3 Selection of Doses in the Study**

All subjects will be assigned to upadacitinib 6 mg BID at the beginning of OLE study. During the course of OLE treatment period the upadacitinib dose can be increased to 12 mg BID based on clinical efficacy assessment and as long as the Investigator has no safety concerns. From January 2017, all subjects who are at Week 72 or beyond will receive once-daily tablet formulation. Subjects who are on 6 mg BID dosing will be transitioned to 15 mg QD dosing. Subjects who are on 12 mg BID dosing will be transitioned to 30 mg QD dosing. The capsule formulation will not be available to subjects once the transition to tablet formulation has occurred.

The change in dose selection in this study is based on extrapolation of pre-clinical efficacy models and analyses of PK, pharmacodynamic, safety, and efficacy data from the Phase 1 studies in healthy volunteers (single and multiple ascending dose Studies M13-401 and M13-845, respectively) and completed Phase 2b randomized, controlled studies (RCTs) in RA subjects (Studies M13-537 and M13-550). The doses selected, 15 mg QD and 30 mg QD, are expected to approximate the exposures achieved with the 6 mg BID and 12 BID immediate release formulations, respectively, which

should be efficacious with an acceptable safety profile. Preliminary results from an ongoing relative bioavailability study demonstrated that single 15 mg and 30 mg doses of the once-daily formulation provide comparable AUC and significantly lower  $C_{max}$  than single doses of 12 mg immediate release (IR) formulation (AUC equivalent to 6 mg BID dose tested in Phase 2) and 24 mg IR formulation (AUC equivalent to 12 mg BID dose tested in Phase 2), respectively, under fasting conditions. At steady-state, the once-daily dose of 15 mg QD is predicted to achieve comparable daily AUC and  $C_{max}$ , and non-inferior  $C_{trough}$  to 6 mg BID IR formulation. In the Phase 2 RCTs, the 6 mg BID dose was shown to achieve the near maximum efficacy. The once-daily dose of 30 mg QD is predicted to achieve comparable daily AUC and  $C_{max}$ , and non-inferior  $C_{trough}$  to 12 mg BID IR formulation. In the Phase 2 RCTs, the 12 mg BID dose was clearly shown to achieve the plateau of efficacy.

Study drug will be given for approximately 312 weeks and will not exceed a dose of 30 mg daily.

## **6.0 Adverse Events**

### **6.1 Complaints**

A Complaint is any written, electronic, or oral communication that alleges deficiencies related to the physical characteristics, identity, quality, purity, potency, durability, reliability, safety, effectiveness, or performance of a product/device after it is released for distribution.

Complaints associated with any component of this investigational product must be reported to the Sponsor (Section 6.2). For adverse events, please refer to Section 6.1 through Section 6.9.

### **6.2 Medical Complaints**

The investigator will monitor each subject for clinical and laboratory evidence of adverse events on a routine basis throughout the study. The investigator will assess and record

any adverse event in detail including the date of onset, event diagnosis (if known) or sign/symptom, severity, time course (end date, ongoing, intermittent), relationship of the adverse event to study drug, and any action(s) taken. For serious adverse events considered as having "no reasonable possibility" of being associated with study drug, the investigator will provide an Other cause of the event. For adverse events to be considered intermittent, the events must be of similar nature and severity. Adverse events, whether in response to a query, observed by site personnel, or reported spontaneously by the subject will be recorded.

All adverse events will be followed to a satisfactory conclusion.

## **6.3 Definitions**

### **6.3.1 Adverse Event**

An adverse event (AE) is defined as any untoward medical occurrence in a patient or clinical investigation subject administered a pharmaceutical product and which does not necessarily have a causal relationship with this treatment. An adverse event can therefore be any unfavorable and unintended sign (including an abnormal laboratory finding), symptom, or disease temporally associated with the use of a medicinal (investigational) product, whether or not the event is considered causally related to the use of the product.

Such an event can result from use of the drug as stipulated in the protocol or labeling, as well as from accidental or intentional overdose, drug abuse, or drug withdrawal. Any worsening of a pre-existing condition or illness is considered an adverse event.

Worsening in severity of a reported adverse event should be reported as a new adverse event. Laboratory abnormalities and changes in vital signs are considered to be adverse events only if they result in discontinuation from the study, necessitate therapeutic medical intervention, (meets protocol specific criteria [see Section 6.10 regarding toxicity management]) and/or if the investigator considers them to be adverse events.

An elective surgery/procedure scheduled to occur during a study will not be considered an adverse event if the surgery/procedure is being performed for a pre-existing condition and

the surgery/procedure has been pre-planned prior to study entry. However, if the pre-existing condition deteriorates unexpectedly during the study (e.g., surgery performed earlier than planned), then the deterioration of the condition for which the elective surgery/procedure is being done will be considered an adverse event.

### **6.3.2 Serious Adverse Events**

If an adverse event meets any of the following criteria, it is to be reported to AbbVie as a serious adverse event (SAE) within 24 hours of the site being made aware of the serious adverse event.

Death of Subject	An event that results in the death of a subject.
Life-Threatening	An event that, in the opinion of the investigator, would have resulted in immediate fatality if medical intervention had not been taken. This does not include an event that would have been fatal if it had occurred in a more severe form.
Hospitalization or Prolongation of Hospitalization	An event that results in an admission to the hospital for any length of time or prolongs the subject's hospital stay. This does not include an emergency room visit or admission to an outpatient facility.
Congenital Anomaly	An anomaly detected at or after birth, or any anomaly that results in fetal loss.
Persistent or Significant Disability/Incapacity	An event that results in a condition that substantially interferes with the activities of daily living of a study subject. Disability is not intended to include experiences of relatively minor medical significance such as headache, nausea, vomiting, diarrhea, influenza, and accidental trauma (e.g., sprained ankle).

**Important Medical Event Requiring Medical or Surgical Intervention to Prevent Serious Outcome**

An important medical event that may not be immediately life-threatening or result in death or hospitalization, but based on medical judgment may jeopardize the subject and may require medical or surgical intervention to prevent any of the outcomes listed above (i.e., death of subject, life-threatening, hospitalization, prolongation of hospitalization, congenital anomaly, or persistent or significant disability/incapacity). Additionally, any elective or spontaneous abortion or stillbirth is considered an important medical event. Examples of such events include allergic bronchospasm requiring intensive treatment in an emergency room or at home, blood dyscrasias or convulsions that do not result in inpatient hospitalization, or the development of drug dependency or drug abuse.

For serious adverse events with the outcome of death, the date and cause of death will be recorded on the appropriate case report form.

#### **6.4 Adverse Events of Special Interest**

The following AEs of special interest will be monitored during the study (see detailed toxicity management in Section 6.10):

- Serious infections, opportunistic infections, herpes zoster, and active TB;
- Malignancy (all types);
- Adjudicated Gastrointestinal perforations;
- Adjudicated cardiovascular events (e.g., major adverse cardiovascular event [MACE]);
- Anemia;
- Neutropenia;
- Lymphopenia;
- Increased serum creatinine and renal dysfunction;
- Hepatic events and increased hepatic transaminases;
- Increased creatine phosphokinase (CPK);

- Adjudicated cardiac, embolic and thrombotic events (non-cardiac, non-CNS).

## 6.5 Adverse Event Severity

The Investigator will classify adverse events according to the Rheumatology Common Toxicity Criteria v.2.0 ([Appendix M](#)).

## 6.6 Relationship to Study Drug

The investigator will use the following definitions to assess the relationship of the adverse event to the use of study drug:

Reasonable Possibility	After consideration of factors including timing of the event, biologic plausibility, clinical judgment, and potential alternative causes, there is sufficient evidence (information) to suggest a causal relationship.
No Reasonable Possibility	After consideration of factors including timing of the event, biologic plausibility, clinical judgment, and potential alternative causes, there is insufficient evidence (information) to suggest a causal relationship.

For causality assessments, events assessed as having a reasonable possibility of being related to the study drug will be considered "associated." Events assessed as having no reasonable possibility of being related to study drug will be considered "not associated." In addition, when the investigator has not reported a relationship or deemed it not assessable, AbbVie will consider the event associated.

If an investigator's opinion of no reasonable possibility of being related to study drug is given, an Other cause of event must be provided by the investigator for the serious adverse event.

## 6.7 Adverse Event Collection Period

[figure not shown]
All adverse events reported from the time of study drug administration (Day 1) until 30 days following discontinuation of study drug administration will be collected, whether

solicited or spontaneously reported by the subject. In addition, serious adverse events will be collected from the time the subject signed the study-specific informed consent.

Adverse event information will be collected as shown in [Figure 2](#), and recorded on the appropriate eCRFs.

**Figure 2. Adverse Event Collection**

Additionally, in order to assist the adjudication process, additional information on any potential cardiovascular events including thromboembolic events will be collected, if applicable.

In the case of any of the following reported events, an appropriate supplemental eCRF should be completed:

- Cardiac events;
- Myocardial infarction or unstable angina;
- Heart failure;
- Cerebral vascular accident and transient ischemic attack;
- Cardiovascular procedures (SAE Supplemental Procedure eCRF);
- Hepatic;
- Renal;
- Herpes Zoster Infection;
- CPK increases considered by the investigator to be an AE;
- Embolic and thrombotic events (non-cardiac, non-CNS);
- COVID-19

Supplemental study case report forms should be completed in the event of COVID -19 related missed/virtual visits, study drug interruptions or discontinuations, or adverse events (including documentation of specific signs/symptoms of infection and testing results).

COVID-19 infections should be captured as adverse events. If the event meets the criteria for a serious adverse event (SAE), then follow the SAE reporting directions per the protocol and above.

The following COVID-19 related supplemental eCRFs should be completed (for both serious and non-serious events):

- COVID -19 Supplemental Signs/ Symptoms
- COVID-19 Status Form

**[contact]**

The sponsor will be responsible for Suspected Unexpected Serious Adverse Reactions (SUSAR) reporting for the Investigational Medicinal Product (IMP) in accordance with Global and Local Regulations. The reference document used for SUSAR reporting in the EU countries will be the most current version of the Investigator's Brochure.

## 6.9 Pregnancy

Pregnancy in a study subject or the partner of an enrolled subject must be reported to AbbVie within 24 hours after the site becomes aware of the pregnancy. Subjects who become pregnant during the study must be discontinued (Section 5.4.1).

Information regarding a pregnancy occurrence in a study subject and the outcome of the pregnancy will be collected after obtaining proper consent.

Pregnancy in a study subject is not considered an adverse event. However, the medical outcome of an elective or spontaneous abortion, stillbirth or congenital anomaly is considered a serious adverse event and must be reported to AbbVie within 24 hours of the site becoming aware of the event.

Subjects should avoid pregnancy throughout the course of the study, starting with the Screening Visit through 30 days after the last study drug administration. Results of a positive pregnancy test or confirmation of a pregnancy will be assessed starting with the Screening Visit through the final study visit.

## 6.10 Toxicity Management

The toxicity management of the AEs including AEs of special interest consists of safety monitoring (review of AEs on an ongoing basis, and periodical/ad hoc review of safety issues by a safety data monitoring committee), interruption of study drug dosing with appropriate clinical management if applicable, and discontinuation of the subjects from study drug. The management of specific AEs and laboratory parameters is described below.

**Serious Infections:** Subjects should be closely monitored for the development of signs and symptoms of infection during and after treatment with study drug. Study drug should be interrupted if a subject develops a serious infection or a serious opportunistic infection. A subject who develops a new infection during treatment with study drug should undergo prompt diagnostic testing appropriate for an immunocompromised subject. As

appropriate, antimicrobial therapy should be initiated, and the subject should be closely monitored. Study drug may be restarted once the infection has been successfully treated. If study drug administration is interrupted for more than 30 days, the subject should be discontinued from the study. Subjects who develop active tuberculosis must be permanently discontinued from study drug.

**COVID-19:** Interrupt study drug in subjects with a confirmed diagnosis of COVID-19. Consider interrupting study drug in subjects with signs and/or symptoms and suspicion of COVID-19. The COVID-19 eCRF must be completed.

**Herpes zoster:** If a subject develops herpes zoster, consider temporarily interrupting study drug until the episode resolves.

**Gastrointestinal Perforation:** If the diagnosis of gastrointestinal perforation is confirmed, (other than appendicitis or mechanical injury) the subject must be discontinued from study drug.

**Cardiovascular Events:** Subjects presenting with potential cardiovascular events should be appropriately assessed and carefully monitored. These events will be reviewed and adjudicated by an independent Cardiovascular Adjudication Committee in a blinded manner.

**Thrombosis Events:** Subjects who develop symptoms of thrombosis should be promptly evaluated and treated appropriately. If the diagnosis of deep vein thrombosis, pulmonary embolus or non-cardiac, non-neurologic arterial thrombosis is confirmed, the subject should be discontinued.

**Malignancy:** Subjects who develop malignancy other than NMSC or carcinoma in situ of the cervix must be discontinued from study drug. Information including histopathological results should be queried for the confirmation of the diagnosis. Periodic skin examination is recommended for subjects who are at increased risk for skin cancer.

**Muscle-related symptoms:** If a subject experiences symptoms suggestive of myositis or rhabdomyolysis consider checking CPK and aldolase, with clinical management and/or study drug interruption as deemed appropriate by the treating physician.

**ECG Abnormality:** Subjects must be discontinued from study drug for an ECG change considered clinically significant and with reasonable possibility of relationship to study drug OR a confirmed absolute QTcF value > 500 msec.

**Management of Select Laboratory Abnormalities:** For any given laboratory abnormality, the Investigator should assess the subject, apply the standard of care for medical evaluation and treatment, following any local guidelines. Specific toxicity management guidelines for abnormal laboratory values are described in [Table 5](#) (confirmation by repeat testing is required) and may require an appropriate supplemental eCRF to be completed. All abnormal laboratory tests that are considered clinically significant by the Investigator will be followed to a satisfactory resolution. If a repeat test is required per [Table 5](#), the repeat testing must occur as soon as possible.

**Table 5. Specific Toxicity Management Guidelines for Abnormal Laboratory Values**

Laboratory Parameter	Toxicity Management Guideline
Hemoglobin	
 
• If hemoglobin < 8 g/dL, interrupt study drug dosing and confirm by repeat testing with new sample.
 
• If hemoglobin decreases <math>\geq 3.0</math> g/dL from baseline without an alternative etiology, interrupt study drug dosing and confirm by repeat testing with new sample.
 
• If hemoglobin decreases <math>\geq 3.0</math> g/dL from baseline and an alternative etiology is known, the subject may remain on study drug at the investigator's discretion.
 
• If confirmed, continue to withhold study drug until hemoglobin value returns to normal reference range or its baseline value.
 

Absolute neutrophil count (ANC)	
 
• If confirmed < 1,000/<math>\mu</math>L, interrupt study drug dosing until ANC value returns to normal reference range or its Baseline value.
 
• Discontinue study drug if confirmed < 500/<math>\mu</math>L by repeat testing with new sample.
 

Absolute lymphocytes counts (ALC)	
 
• If confirmed < 500/<math>\mu</math>L by repeat testing with new sample, interrupt study drug dosing until ALC returns to normal reference range or its Baseline value.
 

Total white blood cell count*	
 
• If confirmed < 2,000/<math>\mu</math>L by repeat testing with new sample, interrupt study drug dosing until white blood cell count returns to normal reference range or its Baseline value.
 

Platelet count	
 
• If confirmed < 50,000/<math>\mu</math>L by repeat testing with new sample, interrupt study drug dosing until platelet count returns to normal reference range or its Baseline value.
 

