**5.2.2                    Exclusion Criteria**

1. Pregnant or breastfeeding female.
2. Ongoing infections at Week 0 that have NOT been successfully treated. Subjects with ongoing infections undergoing treatment may be enrolled BUT NOT dosed until the infection has been successfully treated.
3. Anticipated requirement or receipt of any live vaccine during study participation including up to 30 days after the last dose of study drug.
4. Laboratory values from the visit immediately prior to Baseline Visit\* meeting the following criteria:
  - Serum aspartate transaminase (AST) or alanine transaminase (ALT) > 3.0 × ULN
  - Estimated glomerular filtration rate by simplified 4-variable Modification of Diet in Renal Disease (MDRD) formula < 40 mL/min/1.73m^2

- Total white blood cell count (WBC) < 2,000/ $\mu$ L
- Absolute neutrophil count (ANC) < 1,000/ $\mu$ L
- Platelet count < 50,000/ $\mu$ L
- Absolute lymphocytes count < 500/ $\mu$ L
- Hemoglobin < 8 gm/dL

\*Local requirements may apply. Refer to [Appendix N](#) for local requirements (United Kingdom).

5. Enrollment in another interventional clinical study while participating in this study.
6. Consideration by the investigator, for any reason, that the subject is an unsuitable candidate to receive study drug.

Criteria	Rationale
-----------------	------------------

- |       |  |
|-------|--|
| 1     | The impact of upadacitinib on pregnancy and nursing is unknown |
| 2 – 6 | To ensure safety of the subjects throughout the study          |

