
**Table 5. Specific Toxicity Management Guidelines for Abnormal Laboratory Values (Continued)**

Laboratory Parameter	Toxicity Management Guideline
Serum Creatinine	
 
If serum creatinine is <math>> 1.5 \times</math> the baseline value and <math>> \text{ULN}</math>, repeat the test for serum creatinine (with subject in an euvoletic state) to confirm the results. If the results of the repeat testing still meet this criterion, then interrupt study drug and re-start study drug once serum creatinine returns to <math>\leq 1.5 \times</math> baseline value and <math>\leq \text{ULN}</math>
 
If confirmed serum creatinine <math>\geq 2 \text{ mg/dL}</math>, interrupt study drug and re-start study drug once serum creatinine returns to normal reference range or its baseline value.
 
For the above serum creatinine elevation scenarios, complete supplemental renal eCRF.
 

Creatine Phosphokinase	
 
If confirmed CPK value <math>\geq 4 \times \text{ULN}</math> and there are no symptoms suggestive of myositis or rhabdomyolysis, the subjects may continue study drug at the investigator's discretion.
 
If CPK <math>\geq 4 \times \text{ULN}</math> accompanied by symptoms suggestive of myositis or rhabdomyolysis, interrupt study drug and contact AbbVie Therapeutic Area Medical Director.
 
For the above CPK elevation scenarios, complete supplemental CPK eCRF.
 

\* Local requirements may apply. Refer to [Appendix N](#) for local requirements (United Kingdom).

If the subject must undergo elective surgery, the study drug should be interrupted at least 1 week prior to the surgery. If the subject must undergo emergency surgery, the study drug should be interrupted at the time of the surgery. The study drug can recommence once the physician has examined the surgical site and determined that it has healed and there is no sign of infection.

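### Protocol Table 5, hemoglobin: a fall of 3.0 g/dL or more can still be present when the shared restart line is met, so the end of the interruption is unclear for subjects with a high baseline

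*Protocol*

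**What the plan says.** The hemoglobin row of Table 5 (Protocol Section 6.10) has four bullets.

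- **Absolute trigger.** Below "8 g/dL, interrupt study drug dosing and confirm by repeat testing with new sample".
- **Relative trigger.** A decrease of at least 3.0 g/dL "from baseline without an alternative etiology, interrupt study drug dosing and confirm by repeat testing with new sample". Nothing requires the value to be below the normal range.
- **Discretion.** If the same fall occurs "and an alternative etiology is known, the subject may remain on study drug at the investigator's discretion". This does not reach the case where no other cause is found.
- **Restart, shared by both triggers.** Once confirmed, "continue to withhold study drug until hemoglobin value returns to normal reference range or its baseline value". The two end points are joined by an or, so either is enough.

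The text above the table states that "confirmation by repeat testing is required". Appendix N repeats all four hemoglobin bullets for the United Kingdom.

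At entry, Section 5.2.2 excludes "Hemoglobin < 8 gm/dL". That is a floor only. The UK version of the criterion refers back to the toxicity rules and sets no ceiling on baseline hemoglobin either.

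**The concern.** A restart rule should describe a state in which the reason for stopping has gone. The shared line does this for the absolute trigger. It need not do so for the relative trigger, because a value can be normal and still lie 3.0 g/dL or more below the subject's own baseline.

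Anemia is an adverse event of special interest (Protocol Section 6.4). The study's toxicity scale (Appendix M, row K1; repeated in SAP Appendix C) puts a decrease of 3.0 g/dL or more from pre-treatment in Grade 4, with no reference to the normal range. SAP Section 10.3.4 treats Grades 3 and 4 as potentially clinically significant. Table 5 can therefore be read as allowing restart at a value that the study itself still grades 4.

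What is at stake is consistency between sites. One site may resume dosing once the value is normal. Another may wait for the baseline value and pass the 30-day point in Section 5.5.3, where the investigator decides between restart and discontinuation. The length of interruption, and some discontinuations, would then depend on how the line is read as well as on the subject's hemoglobin.

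**Working it through.** **Inputs from the documents:** the relative trigger, the absolute trigger, the restart line and the entry floor, all as set out above. The documents state no figure for this overlap, so there is none to reproduce.

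**Inputs that must be assumed:** the reference range and the distribution of baseline hemoglobin. Neither is given. Table 5 also does not say which baseline it means: Table 2 footnote a lets the last visit of the preceding trial serve as Week 0, while Section 8.1.3 uses the visit before double-blind treatment for analysis.

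**Logic.** Let B be baseline, H the current value, and L and U the limits of normal.

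- Interruption criterion: B − H ≥ 3.0.
- Restart condition: L ≤ H ≤ U, or H has returned to B.
- A value back at B cannot also be 3.0 below B, so the baseline arm never overlaps with the trigger.
- The normal-range arm overlaps when L ≤ H ≤ B − 3.0. Such values exist if and only if B ≥ L + 3.0. The band is B − 3.0 − L wide.

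**Two examples with an assumed L of 12.0 and B = 15.5** (band 15.5 − 3.0 − 12.0 = 0.5 g/dL wide):

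1. Hemoglobin falls to 11.6 (fall 3.9, below range) and recovers to 12.2. It has returned to normal, so restart is allowed. The fall is still 15.5 − 12.2 = 3.3, so the interruption criterion still holds.
2. Hemoglobin falls to 12.4 (fall 3.1) and never leaves the range. Interruption is required. Whether the restart condition is already met depends on how the word returns is read.

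**Lowest baseline at which overlap occurs** (checked in steps of 0.1 g/dL):

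| Assumed normal range | Lowest baseline with overlap |
|---|---|
| 11.0–15.0 | 14.0 |
| 12.0–16.0 | 15.0 |
| 13.5–17.5 | 16.5 |
| 14.0–18.0 | 17.0 |
| 12.0–14.5 | 15.0 (above normal) |

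A subject with a normal baseline can be affected whenever the range is at least 3.0 g/dL wide. With a narrower range, only baselines above normal are affected.

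**Share of subjects with B ≥ L + 3.0**, assuming a normal distribution, as the upper tail beyond z = (L + 3.0 − mean)/SD:

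| Mean | SD | L | Cut-off | z | Share |
|---|---|---|---|---|---|
| 13.0 | 1.3 | 12.0 | 15.0 | 1.54 | 6.2% |
| 13.0 | 1.3 | 11.5 | 14.5 | 1.15 | 12.4% |
| 13.3 | 1.4 | 12.0 | 15.0 | 1.21 | 11.2% |
| 13.3 | 1.4 | 11.5 | 14.5 | 0.86 | 19.6% |
| 14.3 | 1.4 | 13.5 | 16.5 | 1.57 | 5.8% |
| 14.3 | 1.4 | 13.0 | 16.0 | 1.21 | 11.2% |

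The range is about 6% to 20%. Applied to all 494 subjects, that is 0.058 × 494 ≈ 29 to 0.196 × 494 ≈ 97 with a baseline high enough for overlap.

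**Comparison within the same table.** The absolute trigger has no overlap, because 8 g/dL lies below every lower limit assumed here. The relative creatinine rule has none either. It stops above 1.5 × baseline and above ULN, and it tells sites to "re-start study drug once serum creatinine returns to" at most 1.5 × baseline and at most ULN, so no value satisfies both.

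**The case against.** The strongest reply is linguistic. A value that never left the normal range cannot return to it, and continuing to withhold drug implies that withholding goes on after confirmation. On that reading only the baseline value ends an interruption for a fall that stays in range, and example 2 contains no contradiction. This is a fair reading, but the text does not state it. It also leaves example 1 untouched, and it makes the deeper fall the easier one to restart from: 11.6 needs only to reach 12.0, whereas 12.4 must climb back to 15.5.

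A reader might infer that the fall trigger does nothing for these subjects. The documents do not support that. Dosing stops at the first value, a repeat test on a new sample is required, and Section 6.10 calls for assessment and for follow-up of clinically significant abnormalities. Section 5.4.1 also provides for withdrawal. Repeat testing does not settle when the interruption ends, however, because the confirming value can itself be normal.

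A reader might also infer that drug would cycle on and off. That could happen after example 1, but nothing shows that it would.

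Nor is the hemoglobin safety analysis undermined. The SAP works from laboratory values: mean change (Section 10.3.2), graded shifts (10.3.3) and Grade 3 or 4 listings (10.3.4). Row K1 captures these falls however a site reads the restart line.

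**Conclusion.** The concern holds in a limited form. For any subject with baseline at least 3.0 g/dL above the lower limit of normal, the fall trigger and the shared restart line conflict: clearly so after a drop below the range and a recovery just into it, and ambiguously when the value stays in range throughout. I found nothing elsewhere in the protocol or SAP that resolves this. That the overlap exists follows from the wording and from the absence of an entry ceiling; it does not depend on the assumed figures.

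Its size does depend on them. The 6% to 20% rests on assumed means, SDs and lower limits, each scenario applied to the whole study as one population. It should not be read as 29 to 97 affected subjects. To be affected, a subject must also have a confirmed fall of at least 3.0 g/dL with no alternative cause, and then a value inside the overlap band. The documents give no basis for estimating how often that occurs, only that it must be less often.

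This is an internal inconsistency in a safety rule, narrow in reach, and it should be corrected.

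**What to change.** Reconcile the hemoglobin trigger and restart bullets in Table 5 and in the UK Table 5 of Appendix N, so that no single value meets both the interruption criterion and the restart condition. The wording should also settle what ends the interruption when the value has stayed within the normal range. How to do this, and whether in the trigger, the restart line or both, is for the sponsor's medical team. No threshold or restart rule is proposed here.

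The cost is a short protocol amendment covering two tables. It needs IEC/IRB approval before implementation (Section 9.1) across a study listing 118 sites. With all 494 subjects already enrolled, it can help only in the remaining follow-up. No extra tests, visits or changes to the analysis are needed.
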